3.1. Randomization

In the DBVC period, the Interactive Response Technology system will assign approximately 75 participants in a 2:1 ratio to ruxolitinib 1.5% cream BID and vehicle cream BID, respectively. Additionally, participants will be stratified by face and/or neck IGA score (2 or 3) at screening. Participants with a face and/or neck IGA score of 2 at screening will constitute approximately 25% of the overall study population.

3.2. Control of Type I Error

For the primary analysis, the overall 2-sided Type I error of 0.05 will be used.

3.3. Sample Size Considerations

Approximately 75 participants will be randomized 2:1 (ie, ruxolitinib 1.5% cream BID to vehicle cream BID, respectively). The sample size calculation is based on the Fisher's exact test for the primary efficacy endpoint. Based on the results from the 2 pivotal studies, INCB 18424-303 and -304, the response rate of EASI75 at Week 4 on the head and neck is assumed to be 55% for the active arm of ruxolitinib 1.5% cream BID versus 15% for vehicle cream BID. Using a 2-sided alpha of 0.05, the sample size will have a > 90% power to detect a difference between the ruxolitinib 1.5% cream BID versus vehicle cream BID. In addition, to provide adequate power for efficacy variables, the sample size is determined to provide a large database for safety evaluation.

4. DATA HANDLING DEFINITIONS AND CONVENTIONS

4.1. Scheduled Study Evaluations and Study Periods

4.1.1. Day 1

Day 1 is the date that the first application of ruxolitinib cream or vehicle cream is administered to the participants in the specific period.

4.1.2. Study Day

If a visit/reporting date is on or after Day 1, then the study day at the visit/reporting date will be calculated as

$$\text{Day \#} = (\text{visit/reporting date} - \text{Day 1 date} + 1).$$

If the visit/reporting date is before Day 1, then the study day at the visit/reporting date will be calculated as

$$\text{Day \#} = (\text{visit/reporting date} - \text{Day 1 date}).$$

A study day of -1 indicates 1 day before Day 1.

4.1.3. Baseline Value

Baseline is the last nonmissing measurement obtained before or on the day of first application of ruxolitinib cream or vehicle cream. For safety analyses, participants who cross-over treatment in OL period, baseline is the last nonmissing measurement obtained before or on the first administration of study treatment in OL period.

When scheduled assessments and unscheduled assessments occur on the same day and time of the assessment or time of first application is not available, use the following convention to determine baseline:

- If both a scheduled and an unscheduled visit are available on the day of the first application and the time is missing, use the scheduled assessment as baseline.
- If all scheduled assessments are missing on the day of the first application and an unscheduled assessment is available, use the unscheduled assessment as baseline.

4.1.4. Handling of Missing and Incomplete Data

For response endpoints, all nonresponders, as well as all participants who are missing postbaseline values, will be defined as nonresponders for the NRI analysis.

For other endpoints, missing observations will be handled as detailed in the specific sections addressing each analysis.

4.2. Variable Definitions

4.2.1. Body Mass Index

Body mass index will be calculated as follows:

$$\text{BMI (kg/m}^2\text{)} = [\text{weight (kg)}] / [\text{height (m)}]^2$$

4.2.2. Prior and Concomitant Medication

Prior medication is defined as any nonstudy medication started before the first application of study treatment.

Concomitant medication is defined as any nonstudy medication that is started accordingly:

- Before the date of first application of study treatment and is ongoing throughout the study or ends on/after the date of first application of study treatment.
- On/after the date of first application of study treatment and is ongoing or ends during the course of study treatment.

A prior medication could also be classified as "both prior and concomitant medication" if the end date is on or after the first application of study treatment. In the listing, it will be indicated whether a medication is prior-only, concomitant-only, or both prior and concomitant.

For the purposes of analysis, all medications will be considered concomitant medications unless the medications can unequivocally be defined as not concomitant.

5. STATISTICAL METHODOLOGY

5.1. General Methodology

Unless otherwise noted, SAS® software (SAS Institute Inc, Cary, NC; v9.1) will be used for the generation of all tables, graphs, and statistical analyses. Descriptive summaries for continuous variables will include, but not be limited to the number of observations, mean, standard deviation, median, minimum, maximum, first quartile, third quartile, and 95% CI. Descriptive summaries for categorical variables will include the number and percentage of participants in each category.

5.2. Treatment Groups

This is a randomized, DBVC study followed by an OL period. Data will be summarized based on the treatment (ruxolitinib 1.5% cream BID or vehicle cream BID) that the participant actually applied (ie, FAS).

During the DBVC period, the treatment groups will be ruxolitinib 1.5% cream BID and vehicle cream BID. The treatment groups for the OL period will be ruxolitinib 1.5% cream BID to ruxolitinib 1.5% cream BID, and vehicle cream BID to ruxolitinib 1.5% cream BID.

5.3. Analysis Populations

5.3.1. Full Analysis Set

The FAS will include all participants who are randomized and applied the study drug at least once. Treatment groups for this population will be determined according to the actual treatment the participant applied on Day 1 regardless of assigned study treatment.

The FAS population will be used for the summary of demographics, baseline characteristics, and participant disposition, and analyses of all efficacy and safety data.

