2.2. Objectives and Endpoints

[Table 1](#) presents the objectives and endpoints.

Table 1: Objectives and Endpoints

Objectives	Endpoints
Primary	
To establish the efficacy of ruxolitinib cream in participants with AD on the face and/or neck.	Proportion of participants who achieve an EASI75 of the head and neck region at Week 4.
Secondary	
To further assess efficacy of ruxolitinib cream for the treatment of AD on the face, neck, and other body areas.	Proportion of participants who achieve an EASI75 of the head and neck region at Weeks 2 and 8. Proportion of participants who achieve an overall EASI75 at Weeks 2, 4, and 8.
To assess the safety and tolerability of ruxolitinib in participants with AD on the face and/or neck.	The type, frequency, and severity of AEs, including the evaluation of vital signs.
[REDACTED]	

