6.1. Demographics, Baseline Characteristics, and Disease History

6.1.1. Demographics and Baseline Characteristics

The following demographics and baseline characteristics will be summarized for the FAS population in the DBVC period: age, sex, race, ethnicity, weight, height, and BMI.

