7.3.2. Primary Efficacy Analyses

The primary endpoint is the proportion of participants who achieve EASI75 of the head and neck region at Week 4. The primary analysis will be based on the FAS population in the DBVC period. The primary alternative hypothesis (superiority of ruxolitinib 1.5% cream BID compared with vehicle cream BID) will be tested at a 2-sided $\alpha = 0.05$ level using the CMH test stratified by the stratification factor (ie, the participant's face and/or neck IGA score at screening).

Odds ratio in response rates (ruxolitinib cream vs vehicle) at Week 4 will be computed and provided, as well as the p-values. The difference in proportion of participants who achieve an EASI75 score of the head and neck region (ruxolitinib cream vs vehicle) at Week 4 will also be computed. The 95% CI for the difference will be computed based on a large-sample normal approximation with continuity correction. The p-value and stratum-adjusted EASI75 response rate difference with 95% CI will be provided.

All nonresponders during the DBVC period, as well as all participants who discontinue study treatment at any time before Week 4, or withdraw from the study for any reason, will be defined as nonresponders for the NRI analysis.

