7.3.4. Sensitivity and Supportive Analyses for Primary Endpoint

Not applicable.

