2.1 EASI			
2.1.1	Summary and Analysis of Participants Who Achieved EASI75 of the Head and Neck Region During the Treatment Period	FAS	
2.1.3	Summary and Analysis of Participants Who Achieved an Overall EASI75 During the Treatment Period	FAS	

Exposure and Safety			

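### SAP 5.2 and 5.3.1 group the primary superiority test by the cream applied on Day 1, not by randomised arm, and no as-randomised check is planned

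*SAP*

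**What the plan says.** SAP 5.3.1 admits to the FAS everyone who was randomised and applied study drug at least once. It then sets the grouping rule: "Treatment groups for this population will be determined according to the actual treatment the participant applied on Day 1 regardless of assigned study treatment". That set is to serve demographics, baseline characteristics, disposition and all efficacy and safety analyses. SAP 5.2 states the same as-applied principle for data summaries in general and names the open-label groups by the sequence of creams: "The treatment groups for the OL period will be ruxolitinib 1.5% cream BID to ruxolitinib 1.5% cream BID", with a second group for vehicle followed by ruxolitinib.

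SAP 7.3.2 says: "The primary analysis will be based on the FAS population in the DBVC period". It specifies a two-sided 0.05 CMH test stratified by screening face and/or neck IGA and gives no separate grouping rule for efficacy. The section headed "Sensitivity and Supportive Analyses for Primary Endpoint" (7.3.4) is marked not applicable. Secondary efficacy is descriptive (7.4).

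The SAP is not uniform. Medical history (6.1.4) is summarised by assigned group, and the listing of notable vital signs (8.4) shows the assigned group. Section 6.1.1 ("The following demographics and baseline characteristics will be summarized for the FAS population in the DBVC period") and section 6.2 on disposition carry no grouping rule of their own, so they inherit the as-applied one.

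Protocol Table 8 (section 10.2) defines who is in the FAS and is silent on grouping. Protocol Appendix B, Amendment 2, item 17 explains the FAS: randomisation happens during screening, so an intent-to-treat set could include people who leave before any baseline value exists.

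**The concern.** Randomisation makes the assigned arms comparable. Once a participant is counted in the arm of the cream received, the two groups are no longer the ones that randomisation formed. The comparison then stays unbiased only if the error that put the wrong cream in that participant's hands was unrelated to prognosis. The SAP neither states nor checks that assumption. Grouping by treatment received is normal for safety. Here one set does both jobs, so the safety convention also governs the confirmatory efficacy test.

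The stated reason for the FAS does not reach this choice. Missing baseline values justify requiring at least one application. They say nothing about which arm a dosed participant belongs to. If an error occurred, the medical history table and the demographics table would also show different arm sizes for the same population.

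**Working it through.** **1. The plan's own figure.** Inputs from SAP 3.3: about 75 participants, 2:1, so 50 and 25; response 55% and 15%; two-sided alpha 0.05; Fisher exact test. Exact enumeration gives power of 93.8%, which agrees with the stated figure of more than 90%. That figure is not in dispute.

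**2. Shift in the expected difference when the cream has no effect.** No error rate is given, so one error is assumed. Let p be the common response rate and q the response probability of the misdosed participant, with the vehicle arm's mean held at p. As randomised, the expected difference is 0.

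For a vehicle-assigned participant counted in active, the as-treated difference is

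(50p + q)/51 - (25p - q)/24 = (q - p)(1/51 + 1/24) = (q - p) × 0.0613.

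- p = 15%: q = 0 gives -0.15 × 0.0613 = -0.9 points; q = p gives 0; q = 1 gives 0.85 × 0.0613 = +5.2 points.
- p = 55%: the range is -3.4 to +2.8 points.

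For an active-assigned participant counted in vehicle, it is (p - q)(1/49 + 1/26) = (p - q) × 0.0589. At p = 15% this runs from +0.9 points (q = 0) to -5.0 points (q = 1).

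**3. Chance of a CMH result falsely favouring active.** Assumed strata: 13 against 6 for IGA 2 and 37 against 19 for IGA 3. These follow SAP 3.1 (about 25% IGA 2; 19/75 = 25.3%) and the 2:1 ratio. Response is 15% in both strata, with full enumeration, no continuity correction and two-sided 0.05. Only results favouring active are counted, so the nominal reference is 2.5%, not 5%. One vehicle-assigned participant in the IGA 3 stratum is moved to active.

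| Case | Favours active |
|---|---|
| As randomised, everyone at 15% | 2.0% |
| As treated, error unrelated to prognosis | 1.8% |
| As treated, moved participant fixed beforehand as a certain responder, others at 15% | 2.6% |
| As treated, same, with the other 18 in that stratum lowered to (19 × 0.15 - 1)/18 = 10.3% so that its mean stays at 15% | 5.8% |

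**4. Power if response follows the cream received (55% against 15%).** Same strata and test; without error, power is 94.6%.

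| Vehicle-assigned participants given active (IGA 3) | By assigned arm | By cream applied |
|---|---|---|
| 1 | 92.6% | 94.0% |
| 2 | 89.9% | 93.7% |

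**The case against.** The rule is harmless unless an error happens, and the documents show no error. They describe a single virtual site, central IRT assignment and blinding (Protocol 6.3), and per-participant supply records (Protocol 6.2). If an error is unrelated to prognosis, as a dispensing slip may well be, grouping by cream applied does not inflate false positives (1.8% against 2.0%) and keeps more power. With Fisher's test and one error in each arm, power by assigned arm falls to 90.3%; with two in each arm it falls to 85.6%, against 93.8% by cream applied in both cases. All of this stands. It limits the weight of the point. It does not supply a reason to rest the confirmatory test on an unstated assumption.

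Some stronger readings are tempting but unsupported:

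- A reader might infer that one misdosed participant can raise the false-positive chance for active to 7.0%. That figure arises only if the participant to be moved is picked after the Week 4 outcomes are known. Day 1 application precedes those outcomes, so no dispensing process in the documents could do it.
- A reader might infer that the SAP contradicts the protocol. Table 8 is silent on grouping, so the SAP fills a gap.
- A reader might infer that no other superiority test exists. That can be said only of the visible text: parts of SAP 7.4 and 7.5 are blacked out, as any rationale for the grouping rule may be.
- A reader might infer that the FAS rule plainly governs Week 8 EASI75. Table 1 of the SAP lists "Proportion of participants who achieve an EASI75 of the head and neck region at Weeks 2 and 8", and Appendix A plans "Summary and Analysis of Participants Who Achieved EASI75 of the Head and Neck Region During the Treatment Period" on the FAS. But SAP 5.3.2 assigns all open-label analyses to the OL-evaluable population. The governing set for Week 8 is unclear.

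**Conclusion.** The point holds as a gap worth closing, not as a demonstrated bias. As written, the primary test is not an as-randomised comparison, no as-randomised check is planned, and no visible text justifies moving dosed participants between arms.

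The effect is zero if everyone applies the assigned cream on Day 1. For one vehicle-assigned error under no effect at 15%, the expected difference moves by at most about 5 points. The chance of falsely favouring active lies between 1.8% and 5.8% across the pre-fixed cases examined. These are illustrations under an assumed single error, assumed stratum sizes and equal rates across strata. They do not estimate what will happen.

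**What to change.** In SAP 5.2 and 5.3.1, keep FAS membership as it is (randomised and dosed) and state two grouping rules:

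- **By IRT-assigned arm:** all double-blind-period efficacy analyses, including the primary CMH test with its screening-IGA stratification. Baseline-type FAS summaries should follow the same rule, as 6.1.4 already does.
- **By treatment actually applied:** exposure and safety.

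Place the remaining FAS summaries (protocol deviations in 6.3, medications in 6.6, screening laboratory values in 8.3) under one rule by name, and align the listing wording in 8.4. Label any Week 8 efficacy summary by assigned double-blind arm. Whether the FAS or the OL-evaluable set governs Week 8 should be reconciled separately. The rule should be fixed before anyone knows whether an error occurred, so that the choice cannot depend on the data.

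The cost is a few sentences, and programs that carry both an assigned-arm and an applied-cream variable. Sample size, data collection and conduct do not change. If errors occur and response follows the cream received, the power loss is that shown in step 4 of the working: 1.4 points for one vehicle-assigned error (94.0 - 92.6) and 3.8 points for two (93.7 - 89.9).

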5.3.2. Open-Label Evaluable Population

The OL-evaluable population will include all participants who applied ruxolitinib cream at least once during the OL period.

All analyses for the OL period will be conducted with the OL-evaluable population.

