10.2. Populations for Analysis

The populations for analysis are provided in [Table 8](#).

Table 8: Populations for Analysis

Population	Description
FAS	The FAS includes all participants enrolled in the study who will have at least 1 application of study drug. The FAS will be used for the summary of demographics, baseline characteristics, participants disposition, and analyses of all efficacy and safety data.
OL-evaluable	The OL-evaluable population includes all participants who applied at least 1 dose of ruxolitinib cream during the OL period. All analyses for the OL period will be conducted with the OL-evaluable population.

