3.4 Vital Signs			
3.4.1.1	Summary of Systolic Blood Pressure in the Double-Blind Vehicle-Controlled Period	FAS	X
3.4.1.2	Summary of Systolic Blood Pressure in the Open-Label Period	OL-Evaluable	X

Table No.	Title	Population	Standard
3.4.2.1	Summary of Diastolic Blood Pressure in the Double-Blind Vehicle-Controlled Period	FAS	X
3.4.2.2	Summary of Diastolic Blood Pressure in the Open-Label Period	OL-Evaluable	X
3.4.3.1	Summary of Pulse in the Double-Blind Vehicle-Controlled Period	FAS	X
3.4.3.2	Summary of Pulse Pressure in the Open-Label Period	OL-Evaluable	X
3.4.4.1	Summary of Respiratory Rate in the Double-Blind Vehicle-Controlled Period	FAS	X
3.4.4.2	Summary of Respiratory Rate in Open-Label Period	OL-Evaluable	X
3.4.5.1	Summary of Body Temperature in the Double-Blind Vehicle-Controlled Period	FAS	X
3.4.5.2	Summary of Body Temperature in the Open-Label Period	OL-Evaluable	X

Figures

Figure No.	Title	Population
4.1.1	Proportion of Participants Who Achieved EASI75 of the Head and Neck Region During the Treatment Period	FAS
4.1.3	Proportion of Participants Who Achieved an Overall EASI75 During the Treatment Period	FAS

Listings

Listing No.	Title
2.1.1	Participant Enrollment and Disposition Status
2.1.2	Participant Inclusion and Exclusion Criteria Violations
2.2	Protocol Deviations
2.3	Analysis Population
2.4.1	Demographic Characteristics
2.4.2	Baseline Disease Characteristics
2.4.3	Prior and Concomitant Medications
2.4.4	Prior Medications for Atopic Dermatitis
2.4.5	Medical History
2.5	Study Drug Exposure and Compliance

Listing No.	Title
Efficacy	
2.6.1	Head and/or Neck EASI Score
2.6.2	Total EASI Score
2.6.3	Itch NRS Score
[REDACTED]	[REDACTED]
[REDACTED]	[REDACTED]
[REDACTED]	[REDACTED]
Adverse Events	
2.7.1	Adverse Events
2.7.2	Adverse Events Leading to Drug Discontinuation
2.7.3	Serious Adverse Events
2.7.4	Treatment-Related Adverse Events
2.7.5	Adverse Events With a Fatal Outcome
2.7.6	Adverse Events Leading to Interruption of Study Drug
2.7.8	Adverse Events with Grade 3 or Higher
Laboratory Data	
2.8.1	Clinical Laboratory Values – Hematology
2.8.2	Clinical Laboratory Values – Serum Chemistry
2.8.3	Abnormal Clinical Laboratory Values – Hematology
2.8.4	Abnormal Clinical Laboratory Values – Serum Chemistry
Vital Signs	
2.9.1	Vital Signs
2.9.2	Abnormal Vital Sign Values
2.9.3	Alert Vital Sign Values

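### Do two overlapping population rules in the SAP leave the Week 8 EASI75 denominator open, with an open-label set that depends on outcome?

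*SAP*

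**What the plan says.** Two rules in the SAP cover the same results.

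- SAP 5.3.1: "The FAS population will be used for the summary of demographics, baseline characteristics, and participant disposition, and analyses of all efficacy and safety data".
- SAP 5.3.2: "All analyses for the OL period will be conducted with the OL-evaluable population". Membership needs at least one open-label (OL) application: "The OL-evaluable population will include all participants who applied ruxolitinib cream at least once during the OL period".

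Protocol Table 8 holds both rules, with membership worded almost identically: "The OL-evaluable population includes all participants who applied at least 1 dose of ruxolitinib cream during the OL period".

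SAP Table 1 lists EASI75 at Week 8, for the head and neck and overall, among the secondary endpoints. Week 8 is the end of the OL period. SAP 7.4 makes the secondary endpoints descriptive and names no population.

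SAP Appendix A lists these EASI75 outputs, all on the FAS:

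- Table 2.1.1: "Summary and Analysis of Participants Who Achieved EASI75 of the Head and Neck Region During the Treatment Period"
- Table 2.1.3: "Summary and Analysis of Participants Who Achieved an Overall EASI75 During the Treatment Period"
- Figure 4.1.1: "Proportion of Participants Who Achieved EASI75 of the Head and Neck Region During the Treatment Period"
- Figure 4.1.3: "Proportion of Participants Who Achieved an Overall EASI75 During the Treatment Period"

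SAP 6.2 and Table 1.1.2.2 use the OL-evaluable set for OL disposition.

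**The concern.** Read alone, SAP 5.3 allows two denominators for two named secondary endpoints and states no exception. If the choice were really open, it could be made after the Week 8 data were seen.

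The OL-evaluable set is also not neutral. It omits participants who leave during the double-blind period, whom the FAS counts as nonresponders. It may also omit some of the best responders. Protocol 2.2.1 links continued active treatment to not having cleared by Week 4, and Protocol 4.1 and 6.1 confine OL cream to affected areas. Someone clear everywhere at Week 4 who stays clear might therefore have no OL application. That person would also be missing from the OL disposition table.

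**Working it through.** **The plan's own figure.** The only sample-size figure is power above 90% for 75 participants randomized 2:1 (50 and 25), 55% versus 15%, Fisher's exact test, two-sided 0.05 (Protocol 10.1, SAP 3.3). Exact enumeration gives 93.8%, so the claim is reproduced. It concerns Week 4 and does not depend on this point.

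**How Appendix A uses its period labels.** The exposure tables (3.1.1) and the fifteen adverse event families (3.2.1 to 3.2.15) each come as a set of three, 1 + 15 = 16 sets in all. Every set follows the same pattern:

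| Period named in the title | Population |
|---|---|
| Double-blind vehicle-controlled | FAS |
| Open-label | OL-evaluable |
| Treatment period (both together) | FAS |

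All four visible EASI75 outputs carry the third label and list the FAS. No EASI75 output on the OL-evaluable set is visible. SAP 4.1.4 treats missing postbaseline values as nonresponse for response endpoints. Together these give Week 8 EASI75 on the FAS with nonresponder imputation.

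**What the other denominator would do.** The documents give no Week 8 response rate and no OL entry rate, so all counts below are assumptions.

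*Case 1: everyone left out is a nonresponder.* Let r be the OL-evaluable response rate and s the share of the FAS left out.

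- FAS rate = r × (1 − s), so the gap is r × s.
- s = 4%: 2.0 points at r = 50%, 2.8 at r = 70%.
- s = 10%: 5 to 7 points.
- s = 20%: 10 to 14 points.
- s = 0: no gap.
- Example, vehicle-to-ruxolitinib group: 5 of 25 never apply OL cream and 12 of the other 20 respond. That is 12/20 = 60% against 12/25 = 48%.

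*Case 2: some of those left out are clear responders.* Let N = 50, R = FAS responders, d = double-blind dropouts (nonresponders) and e = participants still clear with no OL application (responders).

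- OL-evaluable rate = (R − e)/(N − d − e).
- This exceeds R/N when e/d < R/(N − R). At 55%, the document's Week 4 assumption, the break-even is 0.55/0.45 = 1.22.

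With R = 28 (FAS 28/50 = 56.0%):

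| d | e | OL-evaluable | Difference from FAS |
|---|---|---|---|
| 5 | 0 | 28/45 = 62.2% | +6.2 |
| 5 | 3 | 25/42 = 59.5% | +3.5 |
| 5 | 6 | 22/39 = 56.4% | +0.4 |
| 5 | 7 | 21/38 = 55.3% | −0.7 |
| 0 | 3 | 25/47 = 53.2% | −2.8 |

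With five dropouts, the sign turns only when 7 of 50 (14%) are clear and untreated for the whole OL period.

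**Disposition.** The number treated in Table 1.1.2.2 is 100% by construction, because treatment defines the set. SAP 6.2 also reports on the FAS who completed the double-blind period (Table 1.1.2.1). Completers minus the OL-evaluable count bounds the number who entered without applying cream. Listing 2.1.1 gives individual enrollment and disposition status.

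**The case for a change.** The strongest argument for a change is that SAP 5.3.1 does not clearly prevail. It also claims disposition and safety for the FAS, yet SAP 6.2 and 8.1 use the OL-evaluable set in the OL period. A programmer extending that pattern could put Week 8 EASI75 on the OL-evaluable set. Appendix A describes its lists as guidance, and one sentence in 5.3.2 would remove the doubt.

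Part of this stands: the two general sentences are not expressly reconciled in the visible body text. The rest is weaker.

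- Appendix A waives an SAP amendment only for list changes that leave the nature of the analysis alone. Moving a named secondary endpoint to another population is hard to fit within that.
- Text around SAP 7.5 is redacted and the table shells are in a separate document, so the visible pages cannot show that nothing else addresses the point.
- The outcome-dependent route is narrow. It needs clearance of every area, not merely a 75% improvement, and no OL application at all. Protocol 6.1 also describes three further days of application after clearing, with an exception at a study visit, so some cleared participants would stay in the set.

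Protocol section 1 reads as twice-daily application for all through Week 8, whereas 2.2.1, 4.1 and 6.1 tie OL application to remaining disease. The schedule note refers the reader to Section 6. These passages must be reconciled as a matter of protocol wording. I take no view on which is right, and the choice of denominator does not turn on it.

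**Conclusion.** The overlap between SAP 5.3.1 and 5.3.2 is real, but it is a gap that an analyst using Appendix A fills correctly: Week 8 EASI75 on the FAS with nonresponder imputation. An added sentence would only repeat in the body what the plan already lists. The disposition point is one of presentation, since the missing information can be recovered from planned outputs.

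The 0 to 14 point range describes an analysis that is not among the visible planned outputs. It rests on assumed response rates of 50% to 70% and assumed non-entry of 0% to 20%, with all those left out counted as nonresponders. The direction is not fixed, and the documents cannot supply the number affected. The conclusion assumes that the analysis follows Appendix A. No change to the plan is needed on this point.
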